8.2 ADVERSE EVENTS AND SERIOUS ADVERSE EVENTS

8.2.1 DEFINITION OF ADVERSE EVENTS (AE)

An adverse event is defined as any untoward medical occurrence associated with the use of the NUTRIPLACE System whether or not the event is considered intervention-related.

8.2.2 DEFINITION OF SERIOUS ADVERSE EVENTS (SAE)

An adverse event (AE) will be considered "serious" if, in the view of either the investigator or sponsor, it results in any of the following outcomes:

- Death
- A life-threatening adverse event
- Inpatient hospitalization or prolongation of existing hospitalization
- A persistent or significant incapacity or substantial disruption of the ability to conduct normal life functions
- A congenital anomaly/birth defect
- Other serious Important medical events that may not result in death, be life-threatening, or require hospitalization may be considered serious when, based upon appropriate medical judgment, they may jeopardize the participant and may require medical or surgical intervention to prevent one of the outcomes listed in this definition.

An unanticipated adverse device effect (UADE) means any serious adverse effect on health or safety or any life-threatening problem or death caused by, or associated with, a device, if that effect, problem, or death was not previously identified in nature, severity, or degree of incidence in the clinical protocol, investigator's brochure, or Instructions for Use (IFU) or any other unanticipated serious problem associated with a device that relates to the rights, safety, or welfare of subjects.

8.2.3 CLASSIFICATION OF AN ADVERSE EVENT

8.2.3.1 SEVERITY OF EVENT

The investigator will categorize the severity of adverse events (AEs) reported in this study using the following definitions:

• **Mild** – Events require minimal or no treatment and do not interfere with the participant's daily activities.

- **Moderate** Events result in a low level of inconvenience or concern with the therapeutic measures. Moderate events may cause some interference with functioning.
- Severe Events interrupt a participant's usual daily activity and may require systemic drug therapy or other treatment. Severe events are usually potentially life-threatening or incapacitating. Of note, the term "severe" does not necessarily equate to "serious".

8.2.3.2 RELATIONSHIP TO STUDY INTERVENTION

The investigator will categorize the relationship of all adverse events (AEs) reported in this study to the NUTRIPLACE System based on temporal relationship and his/her clinical judgment. The degree of certainty about causality will be graded using the categories below.

- **Definitely Related** There is clear evidence to suggest a causal relationship, and other possible contributing factors can be ruled out.
- **Probably Related** There is evidence to suggest a causal relationship, and the influence of other factors is unlikely.
- **Potentially Related** There is some evidence to suggest a causal relationship (e.g., the event occurred within a reasonable time after administration of the trial medication). However, other factors may have contributed to the event (e.g., the participant's clinical condition, other concomitant events).
- Unlikely to be related A clinical event, including an abnormal laboratory test result, whose temporal relationship to study intervention administration makes a causal relationship improbable (e.g., the event did not occur within a reasonable time after administration of the study intervention) and in which other drugs or chemicals or underlying disease provides plausible explanations (e.g., the participant's clinical condition, other concomitant treatments).
- Not Related The AE is completely independent of device and/or evidence exists that the event is definitely related to another etiology. There must be an alternative, definitive etiology documented by the clinician.

In addition, AEs designated as "Definitely", "Probably" or "Potentially" related to the NUTRIPLACE System will be further categorized by the investigator to determine the relationship of the event to the NUTRIPLACE Guidance System based on the following categories:

- Events that likely resulted from insufficient information provided by the guidance system
- Events that likely resulted from inaccurate or confusing information provided by the guidance system
- Events that are not likely related to the guidance system.

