OTHER CONSIDERATIONS	No core lab will be charted for this study; thus, judgements regarding placement will be based on the investigator's assessment of X-Ray images. Assessments of relatedness of any noted adverse events to the study device will be adjudicated by a Clinical Events Committee (CEC). No DSMB will be chartered for this study based on the well- understood safety profile.			
US REGULATORY STATUS	The NUTRIPLACE System is considered a non-significant risk investigational device in the United States.			

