3 OBJECTIVES AND ENDPOINTS

OBJECTIVES	ENDPOINTS	JUSTIFICATION FOR ENDPOINTS
Primary		
The objective of this study is to assess the safety of the NUTRIPLACE System as an adjunct to current practices for placement of nasoenteral feeding tubes.	Procedure success: NET tube can be placed in the correct anatomical position without occurrence of guidance-related adverse events.	This endpoint will support the performance of the NUTRIPLACE System guidance.
Secondary		
There are	e no secondary objectives for this trial	
Tertiary/Exploratory		
Procedure Metrics	Number of placement attempts per patient. Tube migration.	
Safety	Adverse Events	

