6.3 MEASURES TO MINIMIZE BIAS: RANDOMIZATION AND BLINDING

This is an open label, non-randomized feasibility trial with limited bias expected. Bias in this study will be controlled through use of an independent CEC that will review and assess relatedness of reported adverse events to the NUTRIPLACE System.

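### The guidance-causality step has no middle grade, so an adverse event with a possible guidance contribution is probably pooled with unrelated events and left out of the primary-endpoint failures

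*Combined protocol and SAP*

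**What the plan says.** The primary endpoint in section 3, repeated in sections 1.1 and 9.1, is procedure success: "NET tube can be placed in the correct anatomical position without occurrence of guidance-related adverse events". Guidance-related is not defined in any of these places.

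Relation to guidance is graded only in section 8.2.3.2, in two steps.

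- **Step 1, relation to the NUTRIPLACE System.** There are five grades, from Definitely Related to Not Related. The middle one, Potentially Related, needs some evidence of causality and carries the rider "However, other factors may have contributed to the event (e.g., the participant's clinical condition, other concomitant events").
- **Step 2, relation to the guidance system.** Events graded Definitely, Probably or Potentially in step 1 "will be further categorized by the investigator to determine the relationship of the event to the NUTRIPLACE Guidance System based on the following categories". There are three. The first is "Events that likely resulted from insufficient information provided by the guidance system". The second, which concerns misleading displays, is "Events that likely resulted from inaccurate or confusing information provided by the guidance system". The third and last is "Events that are not likely related to the guidance system".

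On adjudication, section 6.3 says "Bias in this study will be controlled through use of an independent CEC that will review and assess relatedness of reported adverse events", meaning relatedness to the NUTRIPLACE System. Sections 1.1 and 10.1.5 likewise give the Clinical Events Committee (CEC) the question of device involvement. None of the three mentions the guidance categories.

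Section 9.4 plans a descriptive calculation of procedure success in every population. Section 9.1 states that there is no formal hypothesis.

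**The concern.** The two steps ask for different strengths of evidence. Some evidence is enough to carry an event into step 2. Once there, the only wordings available are likely and not likely, with no grade for an event where guidance may have contributed but other causes compete.

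Such events are foreseeable. Section 5.1 admits patients who are intubated, sedated or obtunded, and section 2.3.1 lists pneumothorax, pneumonia and aspiration among the risks of tube placement. Those complications can have other explanations in such patients.

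Two things are at stake. First, the only primary endpoint of a study whose objective is safety may be reported somewhat too favourably. Second, once uncertain events share a category with events unrelated to guidance, the guidance category cannot separate them afterwards. With no mapping to the endpoint, borderline cases would be settled after the event is known, in an open-label study.

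**Working it through.** There is no figure in the plan to reproduce. Section 1.1 says the sample size has no statistical basis, and no success threshold or event rate is given. The check is therefore a reading of the scale against the endpoint, followed by a calculation for scale.

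**1. Is there a category for a possible guidance contribution?**

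- Step 1 grades: Definitely, Probably, Potentially, Unlikely, Not Related. A middle grade exists.
- Step 2 categories: likely (insufficient information), likely (inaccurate or confusing information), not likely related. No middle or undetermined grade exists, and there is no instruction for an event that fits neither wording.

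Read literally, anything short of likely goes to the third category.

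**2. Can that category alone decide the endpoint?** Success needs correct position and no guidance-related event. A misplaced tube fails whatever the AE category. But section 2.2 says the real-time trace may lead the user to withdraw and reinsert a tube misdirected into the airway. That patient can end with a correct X-ray and still have an event from the first pass. The position component is then met, and success depends only on whether the event is called guidance-related.

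**3. Does another part of the plan separate these events?**

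- The CEC's stated remit is relatedness to the device or System. The guidance categories are assigned to the investigator. The plan does not say whether a CEC ruling would override them.
- Section 8.2.4 requires every AE to be documented and lists relationship to the NUTRIPLACE System among the items recorded. It does not list the guidance category. The step 1 grade allows a bound, by counting every System-related event as a failure, but it does not identify the events with a possible guidance contribution.

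**4. Size, for illustration.** Inputs: n = 50 patients completing the Procedure Visit (section 9.2), and k = the number of otherwise successful patients whose event would count under a wider rule. The value of k is assumed; the documents give none.

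- Change in success = k/50, so one patient moves it by 1/50 = 2 percentage points.
- Exact (Clopper-Pearson) two-sided 95% intervals for (50 − k)/50:
  - k = 0: 50/50 = 100%; lower limit 0.025^(1/50) = 92.9%
  - k = 1: 49/50 = 98%; interval 89.4% to 99.9% (beta quantiles: lower 2.5% point of Beta(49, 2), upper 97.5% point of Beta(50, 1))

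The ITT and Full Cohort sets also take in screen failures and run-in patients (sections 9.2 and 9.3). Their denominators would be larger and the step per patient slightly smaller.

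**5. Is k = 1 plausible?** The nearest figure is in section 2.2: pulmonary complications in 0.2% to 1.2% of feeding-tube placements. Expected events in 50 patients are 50 × 0.002 = 0.1 to 50 × 0.012 = 0.6. This figure is not specific to this device, covers pulmonary events only, and says nothing about how attribution would be graded. It suggests that even one pulmonary case is uncertain. More than one would probably need other types of AE.

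**The case against.** A reader might infer that the protocol has a rule sending uncertain events to the residual category and scoring them as successes. It has none. No default is written, guidance-related is never tied to the step 2 categories, and an undetermined event strictly fits neither likely nor not likely. An investigator could choose one of the two adverse categories. Harm after a pass with an equivocal trace, for example, could well be classed as arising from insufficient or confusing information. What stands is that the literal wording favours the residual category and nothing in the plan prevents that outcome.

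A reader might also infer a bias of several percentage points. The documents do not support one. They give no rate of uncertain attribution, and the background complication rate makes even one pulmonary case doubtful. With no hypothesis, success threshold or planned confidence interval, the limits above change no decision rule.

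It can further be said that the two steps ask different questions. Step 1 concerns the whole System and step 2 the information it displayed, so requiring likelihood at step 2 is a defensible choice for specificity. Section 2.3.1 lists coughing and minor bleeding as risks of tube placement in general, and a category for anything that cannot be excluded could turn such effects into guidance failures. This stands, and it limits the remedy: such a category would be looser than step 1's own requirement of some evidence.

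Finally, all AEs are recorded and reported, and the CEC reviews relatedness. Both are true. The events stay visible as AEs, but the guidance category still does not set the uncertain ones apart, and the CEC's authority over that category is not stated.

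**Conclusion.** The concern holds as a gap in the scale and in the endpoint definition. Step 2 of section 8.2.3.2 lacks the middle grade that step 1 has. The probable effect is that events with a possible but not likely guidance contribution are pooled with events independent of guidance and left out of the endpoint failures. The effect is inferred from the wording.

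The size is 2 percentage points for each affected patient with a correctly placed tube, on a denominator of 50. One such patient separates a lower limit of 92.9% from one of 89.4%, assuming no other failures. The number of such patients is unknown and may be zero. Type I error and power are not involved; the risk is some upward bias in a descriptive headline figure. This is a cheap improvement worth making before data collection. It does not invalidate the study.

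**What to change.** 1. Add one category to step 2 of section 8.2.3.2: *potentially related to the guidance system*. Define it with step 1's standard, that there is some evidence of a contribution although other factors may also have played a part. Do not word it as cannot be excluded.
2. State in sections 3 and 9.1, before analysis, which step 2 categories count as guidance-related for procedure success, and whether the investigator's or the CEC's classification governs.
3. In section 9.4, report procedure success twice: with only the two likely categories as failures, and with likely plus potentially related events as failures. Give the count in each category.

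The cost is one more CRF tick-box, a few sentences and one more tabulation, with no extra patients. The wider figure may be lower, partly because some routine tube-placement effects may be graded potentially related. Showing both figures lets the reader judge how much that matters.

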8.2.3.3 EXPECTEDNESS

The investigator will be responsible for determining whether an adverse event (AE) is expected or unexpected. An AE will be considered unexpected if the nature, severity, or frequency of the event is not consistent with the risk information previously described for the study intervention in the IB or the instructions for use.

8.2.4 TIME PERIOD AND FREQUENCY FOR EVENT ASSESSMENT AND FOLLOW-UP

The occurrence of an adverse event (AE) or serious adverse event (SAE) may come to the attention of study personnel during study visits and interviews of a study participant or upon review by a study monitor.

AEs not meeting the criteria for SAEs will be captured on the appropriate case report form (CRF). Information to be collected includes event description, time of onset, clinician's assessment of severity, relationship to NUTRIPLACE System, and time of resolution/stabilization of the event. All AEs occurring while on study must be documented appropriately regardless of relationship. All SAEs determined to be related to the NUTRIPLACE System will be followed to adequate resolution or stabilization.

Any medical condition that is present at the time that the participant is screened will be considered as baseline and not reported as an AE. However, if the study participant's condition deteriorates at any time during the study, it will be recorded as an AE.

Changes in the severity of an AE will be documented to allow an assessment of the duration of the event at each level of severity to be performed. AEs characterized as intermittent require documentation of onset and duration of each episode.

8.2.5 ADVERSE EVENT REPORTING

Any reported AE must be reported to Nutriseal via the CRF within 48 hours of the time the Investigator becomes aware of the AE.

Any reported SAE must be reported to Nutriseal via the CRF within 24 hours of the time the Investigator becomes aware of the SAE.

If the Investigator believes that a potential UADE has occurred, Nutriseal must be contacted immediately. In addition, the investigator shall submit to the Nutriseal and to the reviewing IRB a report of any unanticipated adverse device effect occurring during an investigation as soon as possible, but in no event later than 10 working days after the investigator first learns of the effect."

Nutriseal is responsible for conducting an evaluation of an unanticipated adverse device effect and shall report the results of such evaluation to the Food and Drug Administration (FDA) and to all reviewing IRBs and participating investigators within 10 working days after the sponsor first receives notice of the effect. Thereafter, the sponsor shall submit such additional reports concerning the effect as FDA requests.

9 STATISTICAL CONSIDERATIONS

9.1 STATISTICAL HYPOTHESES

There is no formal statistical hypothesis for the primary endpoint of this feasibility trial. The primary endpoint is defined as procedure success, e.g., NET tube can be placed in the correct anatomical position without occurrence of guidance-related adverse events.

9.2 SAMPLE SIZE DETERMINATION

This feasibility trial will include fifty (50) patients completing the Procedure Visit (NasoEnteral Tube placement) and five operators. Each operator must complete training on one run-in subject prior to participating in this study. Patients or patients' LAR who chose not to participate after informed consent but prior to procedure, and patients who because of system malfunction or because of undiscovered or unreported physical reasons (e.g. deteriorating health, anatomical anomalies, mechanical obstruction, etc.) cannot complete the Procedure Visit (NasoEnteral Tube placement) will be considered Screen Failures, not be considered in the total patient count, but will be reported in the ITT dataset as defined below. If less than 45 patients will complete the Follow-up Visit (confirmation of tube tip anatomical location), an enrollment of another 5 patients will be considered.

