1 PROTOCOL SUMMARY

1.1 SYNOPSIS

Study Title	A Feasibilty Study to Evaluate the Clinical Safety of Nutriseal™ Nasoenteral Feeding Tube Placement using the Nutriseal™ NUTRIPLACE System in Patients.	
PROTOCOL NUMBER	NUTRI-001	
DEVICE DESCRIPTION	The Nutriseal [™] NUTRIPLACE [™] System is designed to aid qualified operators in the placement of the Nutriseal [™] NasoEnteral Tube [™] of 10 Fr to 12 Fr into the stomach or small intestine of patients requiring enteral feeding. The NUTRIPLACE System is intended as an adjunct to current placement practices for assisting clinical practitioners who place feeding tubes in adult patients.	
	The Nutriseal [™] NasoEnteral Tube has been specifically designed for use with the NUTRIPLACE [™] System and is intended for placement in the stomach or small intestine. It is intended for use in adult patients who require intermittent or continuous feedings via the nasogastric or nasoenteric route.	
Study Objectives	The objective of this study is to assess the safety of the NUTRIPLACE System as an adjunct to current practices for placement of nasoenteral feeding tubes.	
Study Design	The study is a prospective, single center, non-randomized clinical trial in patients that require placement of a nasoenteral feeding tube as a result of their current medical condition.	
Number of Subjects and Sites	Fifty (50) subjects will complete the Procedure Visit (NasoEnteral Tube placement procedure, section 1.3) at a single center by at least five operators. This number (50 subjects) does not include screen failures. Prior to participating in this trial each operator will place a Nutriseal nasoenteral feeding tubes in a run-in patient to provide training on the use of the NUTRIPLACE System.	
DURATION OF PARTICIPATION/STUDY	Each patient's individual participation will last approximately 20-48 hours. It is expected the entire study will take approximately two (2) months to complete.	
STUDY ENDPOINTS	Primary Endpoint:	
	Procedure success: Nasoenteral tube (NET) can be placed in the correct anatomical position without occurrence of guidance-related adverse events.	
	Additional Assessments:	

	Procedure Metrics: Number of placement attempts required				
	Safety: Adverse Events				

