Sample Size Considerations	There is no statistically based sample size for this study which is being conducted to obtain confirmatory evidence to support the safety of using the NUTRIPLACE System as an adjunct to current placement practices for nasoenteral feeding tubes. Fifty (50) patients completing the Procedure Visit (NasoEnteral Tube placement procedure) will provide evidence that the NET tube guidance system does not present new or different safety issues as compared to the predicate (confirmatory study). If less than 45 patients will complete the Follow-up Visit (confirmation of tube tip anatomical location, section 1.3), an enrollment of another 5 patients will be considered.				
SCHEDULED VISITS	This study is an acute safety assessment of the NUTRIPLACE System covering the guidance functionality of the System.				
	Screening The screening visit will occur at time zero and will assess eligibility for the study and obtain informed consent.				
	Procedure The study procedure may occur within two days of screening. Informed consent will affirmed and the patient will be considered enrolled.				
	Final Follow Up The final follow-up visit will occur 20-48 hours following the procedure.				
INCLUSION CRITERIA	 Patients must be ≥21 years of age Patients must require placement of a nasoenteral feeding tube Patients have an endotracheal tube, OR Do not have an endotracheal tube but are sedated and/or classified as obtunded¹ at the time of placement Patients or legal authorized representative must be able to understand and adhere to all protocol procedures and be willing and able to provide written informed consent² 				
Exclusion Criteria	 Patients must not have a history of: Esophageal varices or ulcers Upper airway obstruction Upper GI stenosis or obstruction 				

Obtundation level evaluation is based on Glasgow-Coma scale with a score of between 9 and 12. Sedation level is based on Richmond Agitation-Sedation Scale (RASS) score of -2 or less.
 ² Consent may be provided by patient's legal authorized representative.

	 Trauma involving sinuses, nares face or neck that would prevent NG tube insertion Deformities of the sinus cavities and/or skull base Esophageal cancer or neoplasm Patients must not have a significant concomitant illness that would adversely 			
	affect their participation in the study			
	Female patients who are pregnant or lactating			
STATISTICAL ANALYSIS	All data will be reported using summary statistics.			

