5.2 EXCLUSION CRITERIA

Candidates for this study must not meet any of the following exclusionary criteria in order to be enrolled in this trial.

- Patients must not have a history of:
 - Esophageal varices or ulcers
 - Upper airway obstruction
 - Upper GI stenosis or obstruction
 - Trauma involving sinuses, nares face or neck that would prevent NG tube insertion
 - Deformities of the sinus cavities and/or skull base
 - Esophageal cancer or neoplasm
- Patients must not have a significant concomitant illness that would adversely affect their participation in the study
- Female patients who are pregnant or lactating

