5.4 SCREEN FAILURES

Screen failures are defined as participants who consent to participate in the clinical trial but are not subsequently entered in the study and do not complete the Procedure Visit. A minimal set of screen failure information is required to ensure transparent reporting of screen failure participants, to meet the Consolidated Standards of Reporting Trials (CONSORT) publishing requirements and to respond to queries from regulatory authorities. Minimal information includes demography, screen failure details, eligibility criteria, and any serious adverse event (SAE).

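### Failed placements are labelled Screen Failures yet reported in ITT, and the plan does not state how they count in the procedure-success rate

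*Combined protocol and SAP*

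**What the plan says.** Section 9.2 sets a target of 50 completed procedures and names two groups that fall outside it. One is patients, or their representatives, "who chose not to participate after informed consent but prior to procedure". The other is "patients who because of system malfunction or because of undiscovered or unreported physical reasons" cannot finish the placement visit. Both groups "will be considered Screen Failures, not be considered in the total patient count, but will be reported in the ITT dataset as defined below". The synopsis (1.1) agrees on the count: "This number (50 subjects) does not include screen failures".

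Other places that bear on the point:

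- **1.1, Scheduled Visits**, under Procedure: "Informed consent will affirmed and the patient will be considered enrolled".
- **1.2, Figure 1** shows Enrollment as its own step ahead of Procedure, and speaks of enrolling fifty patients rather than of fifty completing.
- **5.4** describes screen failures as consenting participants who "are not subsequently entered in the study and do not complete the Procedure Visit". The minimum data for them are demography, failure details, eligibility and any SAE. Non-serious events are not listed.
- **9.3** defines ITT as everyone enrolled, Per-Protocol as enrolled patients without a noted deviation, and Full Cohort as ITT plus run-ins.
- **9.1** defines success: "NET tube can be placed in the correct anatomical position without occurrence of guidance-related adverse events". Section 9.4 calculates it in every population.

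No section says how a patient without a placement is scored, or which population gives the main result.

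**The concern.** A malfunction that prevents placement is one of the outcomes that a device feasibility study most needs to count. Calling it a screening failure puts it in a category that section 5.4 keeps for people who never entered the study. That label could later be used to leave such patients out of the success rate, or to collect too little on them: the endpoint turns on any guidance-related adverse event, but the minimum data set names only serious ones.

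In the other direction, section 9.2 reports in ITT people who withdrew before anything was attempted. If they were counted as failures, the rate would fall for reasons unrelated to the device.

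The trial has no hypothesis and no success threshold, so this descriptive rate is its main result. It should have one denominator and one scoring rule, both fixed before the data are seen.

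**Working it through.** **Step 1. Set the rules side by side.** There is no planned figure to reproduce: 1.1 says that the 50 has no statistical basis, and the plan specifies no confidence interval.

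| Patient | 9.2 | 1.1 (Scheduled Visits) with 9.3 | 5.4 |
|---|---|---|---|
| Reached the procedure, placement not completed | Screen Failure, reported in ITT | Enrolled, so in ITT | Label does not fit a patient who has entered the study |
| Withdrew after consent, before the procedure | Screen Failure, reported in ITT | Not enrolled if enrolment happens at the procedure, so not in ITT | Label fits |

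*Row 1.* Three sections agree on ITT membership. The conflict is with the label and with the reduced data that come with it.

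*Row 2.* The conflict is over ITT membership itself. It depends on the enrolment point, on which 1.1 and Figure 1 differ. If enrolment is a step before the procedure, as Figure 1 shows, a patient who withdraws between the two steps could be enrolled. A patient who declines when consent is re-affirmed would not be.

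**Step 2. Check the scoring.** Under 9.1, a tube that was attempted and not placed cannot meet the definition, so non-success is implied, though not stated. For a patient in whom nothing was attempted, nothing is implied.

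**Step 3. Check whether the other populations settle it.** Per-Protocol is a subset of enrolled patients and Full Cohort is ITT plus run-ins, so both inherit the question. Section 10.1.9 defines a deviation as noncompliance, and a malfunction is not clearly that.

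**Step 4. Size.** All counts here are assumptions, because the documents give none: 48 successes among 50 completers, k failed placements, and w decliners. The rate is x/n. The interval is the exact (Clopper-Pearson) two-sided 95% interval, with lower limit the 0.025 quantile of Beta(x, n − x + 1) and upper limit the 0.975 quantile of Beta(x + 1, n − x).

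| Assumption | Rate | Exact 95% CI |
|---|---|---|
| k = 0, or failed placements left out or set to missing | 48/50 = 96.0% | 86.3 to 99.5 |
| k = 1, counted as failure | 48/51 = 94.1% | 83.8 to 98.8 |
| k = 3, counted as failures | 48/53 = 90.6% | 79.3 to 96.9 |
| k = 3 and w = 2, all counted as failures | 48/55 = 87.3% | 75.5 to 94.7 |

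Three failed placements move the rate by 96.00 − 90.57 = 5.43 points. Two decliners scored as failures, which no section asks for, would move it by a further 90.57 − 87.27 = 3.30 points. If no placement fails and nobody declines, every reading gives the same rate.

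**The case against.** The strongest reply is that the main case is already handled. Section 9.2 sends malfunction and physical-reason cases to ITT by name, 1.1 and 9.3 agree, and 9.4 calculates success in ITT. Section 9.1 implies that an attempted placement that fails is not a success. Section 5.4 defines a label and its minimum reporting and does not mention ITT, so the specific rule in the statistical section should prevail over it. All of this stands.

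It follows that a reader might infer too much in three ways:

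- **That the plan drops device failures from its analysis, so its success rate is biased upward.** The documents do not support this. A completers-only rate is not a planned population, and it arises only if 5.4 is taken to override 9.2.
- **That leaving these patients outside the 50 is itself an error.** It is not. The 50 is a recruitment target, and replacing non-completers is compatible with analysing them.
- **That decliners are plainly not enrolled.** Figure 1 leaves room for some of them to be.

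What the reply does not remove is the misfit between label and definition, the reduced data set attached to that label, the unsettled enrolment point, and the missing scoring rule. Section 8.2.4 requires all on-study adverse events to be documented, but whether a patient relabelled as a screen failure is on study is the open question.

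**Conclusion.** The wording is wrong as it stands and should be corrected. It contains two specific conflicts: the Screen Failure label in 9.2 against its definition in 5.4, and decliners reported in ITT under 9.2 against enrolment in 1.1 and ITT in 9.3, with Figure 1 pointing to a different enrolment step. It also has a gap, because non-success is implied but unstated for attempted placements, and nothing is said for patients never attempted.

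The size depends on counts that the documents do not give. Under the assumed three failed placements it is about 5 points on the main rate; with none it is zero. No decision threshold is affected, because the trial has none. What is at stake is whether the reported rate can be read in only one way.

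**What to change.** Reword sections 1.1, 1.2, 5.4, 9.2 and 9.3 together:

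1. State one enrolment point. Limit Screen Failure to consented patients in whom neither System set-up nor tube insertion was begun. List these patients, including decliners, but keep them out of the success denominator.
2. Calculate the main success rate in all non-run-in patients in whom set-up or insertion was begun. Either call this an attempted-procedure set or redefine ITT to mean it. Build Per-Protocol and Full Cohort on it, and list separately any enrolled patients in whom nothing was attempted.
3. Count malfunction and non-placement in that set as procedure failure, with the reason listed. Some physical-reason cases may prove to be ineligibility found late, for example "Upper GI stenosis or obstruction" in section 5.2. Add a sensitivity analysis without patients later found to have met an exclusion criterion.
4. Collect full procedure and adverse-event data on attempted but failed placements, not the minimum set in 5.4.

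The target of 50 completed procedures can stay. The cost is rewording in five sections and a little more data on the few failed attempts; the reported rate may be slightly lower.
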